5 ENDPOINTS

5.1 Primary Endpoint

The primary endpoint for this trial is defined as the patient-oriented composite endpoint (PoCE) at 12 months post-procedure. PoCE is a composite measure of

- All-cause mortality
- Stroke (modified Rankin Scale (mRS≥1)
- Any Myocardial Infarction* (includes nontarget vessel territory)
- Any unplanned revascularization for ischemia (includes all target and nontarget vessels)

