5.2 Secondary Endpoints at all follow-up visits/contacts

1. Composite Endpoints

- Patient Oriented Composite Endpoint (PoCE) defined as the composite of all-cause death, stroke, any MI*, and any revascularization (for all follow-up contacts other than 12 months)
- Target Vessel Failure (TVF) defined as cardiac death, TV MI*, and clinically indicated target vessel revascularization
- TLF (DoCE) defined as cardiac death, TV MI* and clinically-indicated target lesion revascularization (DoCE will be reported both including the left-main target lesion only and all target lesions)

2. Mortality

- All death
- Cardiac death
- Non-cardiac death (vascular and non-cardiovascular)

3. Stroke

- All
- Ischemic
- Hemorrhagic

4. Myocardial Infarction*

- All MI (periprocedural, spontaneous, Q-wave and non Q-wave),
- Target Vessel/ Non-Target Vessel MI

5. Revascularization

- Any revascularization
- Target Lesion revascularization (TLR) (any, clinically-indicated TLR, non-clinically indicated TLR) TLR will be reported both including the left-main target lesion only and all target lesions)
- Target Vessel revascularization (TVR) (any, clinically-indicated TVR, non-clinically indicated TVR)
- Non-Target Vessel revascularization

6. Stent thrombosis according to ARC classification

* Definition EXCEL study (APPENDIX I: Definitions)

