7.10 Unscheduled Angiography/Intervention

For all unscheduled angiographies and revascularizations, the angiogram must be sent to the CRO, regardless of whether target or non-target vessel revascularization was performed. The Clinical Event Committee (CEC) will adjudicate the type of revascularization indicating if the revascularization is clinically indicated or not clinically indicated, etc. (See Appendix I:

Definitions). Routine follow-up angiography (in the asymptomatic patient) is not permitted in this study and the reasons for follow-up angiography will be closely tracked in the case report form.

In patients who do undergo follow-up angiography, repeat PCI or CABG may only be performed with evidence of ischemia, requiring one of the following to be present:

- $\geq 70\%$ diameter stenosis of the treated or new lesions by visual angiographic assessment
- In the case of a visually estimated diameter stenosis of $\geq 50\%$ to $< 70\%$, either
 - evidence of definite ischemia in the territory of the diseased vessel by prior non-invasive stress* testing with imaging evaluation showing ischemia in the questioned myocardial territory, and/or
 - IVUS minimal stent area $\leq 6.0 \text{ mm}^2$ for left main lesions or $\leq 4.0 \text{ mm}^2$ for non left main lesions, and/or
 - intra-procedure FFR ≤ 0.80 /iFR ≤ 0.89 .

*stress test is not advised within 8 weeks after stent implantation.

IVUS is preferred for assessment of left main lesions, and iFR is preferred for assessment of non-left main lesions. In particular, after left main stent implantation, the ostial LCX may often appear significantly or even severely stenosed in the absence of symptoms or ischemia (“pseudostenosis”). All patients with a suspected ostial LCX stenosis, regardless of the degree of angiographic severity (unless occluded), are highly recommended to have demonstrated an iFR ≤ 0.89 (or FFR ≤ 0.80 when available) in the LCX prior to repeat revascularization, unless there is unequivocal evidence of lateral wall ischemia on non-invasive stress testing.

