8.2 Sample Size Calculations

Assumptions:

Power = 80%

One-sided alpha = 5%

Non-inferiority margin of 6.3%

XIENCE PoCE – 16.7% at 12M (Reference: EXCEL study, PCI cohort, data on file).

Confidential and Proprietary

Do not distribute or reproduce without the prior written permission of ECRI.

Protocol Version 1.2 – 02 Oct 2018

The BiOSS LIM C expected PoCE assumption is based on an assumed no difference in event rate as compared to the objective performance goal (OPC – EXCEL study).

A sample size calculation of 256 analyzable patients is required using the assumptions above, PASS software, and a non-inferiority Fisher Exact test for one proportion. This number is increased to 260 patients accounting for some attrition.

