- *When biomarker levels are stable or falling*, there should be new CK-MB elevation by an absolute increment of $\geq 10 \times \text{ULN}$ (or $\geq 70 \times \text{ULN}$ for cTnI or T) from the previous nadir level
- *When biomarker levels have not been shown to be stable or falling*, there should be a further rise in CK-MB or troponin beyond the most recently measured value by an absolute increment of $\geq 10 \times \text{ULN}$ in CK-MB or $\geq 70 \times \text{ULN}$ in cTn plus new ST-segment elevation or depression plus signs consistent with a clinically relevant MI, such as new onset or worsening heart failure or sustained hypotension.

While not currently recommended as part of this definition, use of post-CABG ECGs, indices of hemodynamic instability, and imaging studies demonstrating new wall motion abnormalities are suggested to complement biomarker elevations post- CABG to improve specificity.

REVASCULARISATION

[Target Lesion]

A lesion revascularized in the index procedure (or staged procedure). The left-main target lesion extends from the distal left main stem to the end of the 5 mm proximal segments of the left anterior descending and left circumflex arteries as well as the ramus intermedius if the latter vessel has a vessel diameter of ≥ 2 mm.

[Target Vessel]

The target vessel is defined as the entire major coronary vessel proximal and distal to the target lesion including upstream and downstream branches and the target lesion itself. The left main

and any vessel originating from the left main coronary artery or its major branches is, by definition, considered a target vessel for the purposes of this trial (unless either the LAD or LCX are occluded at baseline and no attempt was made to revascularize these territories by PCI).

[Target Vessel-Non-Target Lesion]

The target vessel but non-target lesion consists of a lesion in the epicardial vessel/branch that contains the target lesion; however, this lesion is outside of the target lesion by at least 5 mm distal or proximal to the target lesion determined by coronary angiography.

[Non-Target Vessel]

For the purposes of this trial, the only possible non-target vessel would be the right coronary artery and its major branches that were not treated by PCI at the index procedure (unless either the LAD or LCX are occluded at baseline and no attempt was made to revascularize these territories by either PCI or CABG).

[Target Vessel Revascularization (TVR)]

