Target vessel revascularization is any repeat percutaneous intervention of the target vessel or bypass surgery of the target vessel.

[Target Lesion Revascularization (TLR)]

Target lesion revascularization is defined as any repeat percutaneous intervention of the target lesion or bypass surgery of the target vessel.

[Clinically-Indicated Revascularization (CI-TLR/TVR)]

Revascularization will be considered ischemia-driven if the target lesion diameter stenosis is $\geq 50\%$ by QCA and any of the following criteria for ischemia are met:

- Positive functional ischemia study including positive FFR/iFR corresponding to the area served by the target lesion; or
- Ischemic ECG changes at rest in a distribution consistent with the target vessel; or
- Typical ischemic symptoms referable to the target lesion; or
- IVUS of the target lesion with a minimal lumen area (MLA) of $\leq 4\text{mm}^2$ for non left main lesions or $\leq 6\text{mm}^2$ for left main lesions. If the lesions are de novo (i.e. not restenotic), the plaque burden must also be $\geq 60\%$; or
- FFR of the target lesion ≤ 0.80 or iFR of the target lesion ≤ 0.89 .

A target lesion revascularization for a diameter stenosis less than 50% might also be considered ischemia-driven by the Clinical Events Committee if there was a markedly positive functional study or ECG changes corresponding to the area served by the target lesion.

STENT THROMBOSIS

(ARC)⁴²

Stent thrombosis should be reported as a cumulative value at the different time points and with the different separate time points. Time 0 is defined as the time point after the guiding catheter has been removed and the patient left the catheterization lab.

Timing:

- Acute stent thrombosis*: 0 - 24 hours post stent implantation
- Subacute stent thrombosis*: >24 hours - 30 days post stent implantation
- Late stent thrombosis†: 30 days - 1 year post stent implantation
- Very late stent/ thrombosis†: >1 year post stent implantation

* Acute/subacute can also be replaced by early stent thrombosis. Early stent thrombosis (0 - 30 days) - this definition is currently used in the community.

† Including “primary” as well as “secondary” late stent thrombosis; “secondary” late stent thrombosis is a stent thrombosis after a target segment revascularization.

Categories:

- Definite
- Probable
- Possible

Definitions of each category are as follows.

- **Definite stent thrombosis**

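### Appendix I ties clinically indicated TVR to stenosis of the target lesion, so TVF collapses to essentially TLF; separately, the ischemia condition in the primary PoCE is undefined.

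*Combined protocol and SAP*

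**What the plan says.** Appendix I (Revascularisation) contains a single rule for clinically indicated revascularization, and its heading names both CI-TLR and CI-TVR. It opens: "Revascularization will be considered ischemia-driven if the target lesion diameter stenosis is" at least 50% by QCA, and then asks for one of five signs of ischemia. Four of the five refer to the target lesion; the resting-ECG criterion alone refers to the target vessel. One exception lets the CEC accept a stenosis below 50%, but only for a target lesion revascularization.

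The same appendix defines a target lesion as "A lesion revascularized in the index procedure (or staged procedure"), and gives the left-main target lesion anatomical limits. It has a separate category for a lesion in the target vessel at least 5 mm away from the target lesion.

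Two endpoints depend on how a revascularization is classified:

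- Section 5.2: "Target Vessel Failure (TVF) defined as cardiac death, TV MI*, and clinically indicated target vessel revascularization".
- Section 5.1, a component of the primary PoCE: "Any unplanned revascularization for ischemia (includes all target and nontarget vessels").

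Section 7.10, which covers target and non-target vessels alike, says: "The Clinical Event Committee (CEC) will adjudicate the type of revascularization indicating if the revascularization is clinically indicated or not clinically indicated, etc", and points to Appendix I.

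**The concern.** TVF exists alongside DoCE/TLF because it should also capture clinically driven procedures in the target vessel but outside the treated lesion. If the only rule for clinical indication looks at the target lesion, that extra part has no route in. TVF then repeats DoCE under another name, and a TVR done for real ischemia is tabulated as not clinically indicated.

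The primary endpoint raises a related question. It requires ischemia, but neither Section 5.1 nor Appendix I says how that is decided for the PoCE. The one adjudication rule in the protocol that uses ischemia language is the target-lesion rule. In a single-arm trial judged against a fixed number, a narrower count in this trial than in the benchmark moves the result towards success.

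**Working it through.** **1. Tracing one case through the definitions.** Take a patient with a patent left-main target lesion (under 50% by QCA), angina, and repeat PCI of a new, tight mid-LAD lesion.

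- Location: the mid-LAD is in the target vessel, and the lesion lies more than 5 mm from the target lesion. The procedure is a TVR and not a TLR.
- Entry condition: the target lesion is under 50%. Not met.
- Ischemia criteria: these add to the entry condition, so even the ECG criterion worded by target vessel does not help.
- Exception: limited to target lesion revascularization. Not available.

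No stated criterion makes this procedure clinically indicated.

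**2. Effect on TVF.** The two composites share cardiac death and target vessel MI:

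- DoCE/TLF (all target lesions) = cardiac death + TV-MI + CI-TLR
- TVF = cardiac death + TV-MI + CI-TVR

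Every CI-TLR is also a CI-TVR. If CI-TVR outside the target lesion has no route in, CI-TVR reduces to CI-TLR and the two composites coincide. They coincide *essentially* rather than exactly. A new lesion could pass if the target lesion also happened to be at least 50% stenosed. Bypass of the target vessel is classed as TLR by definition, so the discretionary exception could reach it.

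**3. The plan's own sample size.** Inputs from Section 8.2: reference rate 16.7%, "Non-inferiority margin of 6.3" percentage points, "One-sided alpha = 5"%, power 80%, expected rate equal to the reference. The target is 16.7% + 6.3% = 23.0%.

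n = [(1.645·√(0.23·0.77) + 0.842·√(0.167·0.833)) / 0.063]² = [(0.692 + 0.314) / 0.063]² = 255.04, rounded up to **256**. The stated figure reproduces, and this point does not alter it.

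**4. Size of the conditional risk to the primary endpoint.** With complete follow-up, the Kaplan-Meier limit of Section 8.1 is k/n + 1.645·√(p(1−p)/n), where p = k/n. At n = 260:

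- k = 49: 0.1885 + 1.645 × 0.0243 = 0.228, below 0.23, so success
- k = 50: 0.1923 + 1.645 × 0.0244 = 0.233, above 0.23, so failure

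Success needs at most 49 event patients. Let the true PoCE rate be 23%, and let some patients have ischemia-driven revascularization outside the target lesion as their only event, left uncounted:

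| Uncounted (points) | Patients of 260 | Observed rate | P(X ≤ 49), n = 260 | Same limit, n = 256 | Exact test, n = 256 (≤ 47 events) |
|---|---|---|---|---|---|
| 0 | 0 | 23% | 6.2% | 5.9% | 4.3% |
| 1 | 2.6 | 22% | 12.3% | 11.8% | 9.0% |
| 2 | 5.2 | 21% | 22.0% | 21.1% | 16.9% |
| 3 | 7.8 | 20% | 35.4% | 34.1% | 28.5% |

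The 1 to 3 points are an assumption; the documents give no rate for such events.

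**The case against.** A reader might infer that events outside the target lesion *will* drop out of the primary endpoint. The documents do not support that. Section 5.1 expressly includes all target and nontarget vessels, uses neither *clinically indicated* nor *ischemia-driven*, and does not cite the Appendix I rule. That rule is headed for TLR and TVR only and does not claim to cover an untreated right coronary artery. What stands is narrower: the ischemia condition is undefined, and Section 11.3 leaves the classification algorithm to a later CEC Charter.

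A reader might also infer that TVR is emptied from TVF, or that a new lesion can never qualify. Both go too far. Target lesion events stay in TVF, and the rule says *if*, not *only if*.

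Nor does the IVUS criterion ("If the lesions are de novo (i.e. not restenotic), the plaque burden must also be" at least 60%) prove the rule self-contradictory. The left-main target lesion is defined by anatomy, including the first 5 mm of the LCX. New disease in an unstented ostial LCX can therefore be de novo and still lie inside it.

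Section 7.10 does list evidence of ischemia for treated or new lesions. It does so as a condition for performing repeat PCI or CABG, not as an endpoint definition, and its thresholds differ from Appendix I: a visual stenosis of at least 70% is sufficient alone there. It shows that the protocol has new lesions in view but does not fill the gap.

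On direction, the 16.7% is data on file and its counting rule is not shown. If the benchmark was counted equally narrowly, the bias shrinks or disappears. Finally, any TVR, non-clinically indicated TVR and any revascularization are all reported, so misclassified events remain visible. Non-target vessel revascularization carries no clinical-indication qualifier and is unaffected.

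**Conclusion.** The definitional gap is real and follows from the text alone: as written, clinically indicated TVR reduces to clinically indicated TLR, TVF becomes essentially DoCE/TLF for all target lesions, and the clinically versus non-clinically indicated TVR split is mislabelled. This assumes only that the CEC applies Appendix I as Section 7.10 directs.

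The primary-endpoint risk is conditional. It needs the CEC to borrow the target-lesion rule for the undefined ischemia condition, and a benchmark that was counted more fully. If both hold, with n = 260, complete follow-up and a true rate of 23%, the chance of success rises from about 6% to 12%, 22% or 35% for an assumed 1, 2 or 3 points uncounted.

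**What to change.** In Appendix I, key the entry condition and the criteria for CI-TVR to the lesion being revascularized, or the territory it serves. Keep the target-lesion wording for CI-TLR.

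Before any adjudication, state which rule decides the ischemia condition in the PoCE for all target and nontarget vessels. Make it consistent with how the 16.7% EXCEL benchmark was counted; that counting rule should be obtained and written down. Reconcile Sections 5.1, 5.2 and 7.10, Appendix I and the CEC Charter, saying explicitly whether the Section 7.10 list has any role in endpoint classification.

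The cost is a paragraph in Appendix I, a sentence in Section 5.1 and matching Charter text. No new data and no change to the sample size are needed. TVF counts, and possibly PoCE counts, may come out slightly higher. Settling this before events are known avoids a definition that could be challenged as data-driven.

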19 APPENDIX III: IFR ACQUISITION PROTOCOL

0. give NTG, at least 60 seconds before performing measurements.
1. connect wire
2. wait for wire to stabilize
3. insert wire in guiding catheter
4. advance pressure sensor of pressure wire to end of guide catheter
5. zero aortic pressure to atmospheric pressure [PA ZERO]
6. normalize aortic pressure to distal pressure measurement [NORMALIZE]
7. screenshot or short recording, do recording in FFR mode

[LAD]

8. advance pressure wire distal to the bifurcation stenosis in main branch (e.g. LAD)
9. wait for 10 sec for any reactive hyperemia (e.g. due to contrast injection)
10. measure iFR twice (to uncover any upward drift of the value due to remaining reactive hyperemia)
11. measure Pd/Pa in 'FFR mode' for 20 seconds without inducing hyperemia
12. keep wire in position, record angiogram with sufficient contrast filling
13. go in orthogonal view, keep wire in original position, acquire angiogram
14. wait for 10 sec for any reactive hyperemia (e.g. due to contrast injection)
15. measure iFR pullback and record angiogram during the pullback. Retract the wire into guiding catheter
16. screenshot or short recording to confirm absence of drift, perform recording in 'FFR mode' (if drift is more than +/- 0.02, redo normalization and measurement)

[LCX]

17. advance pressure wire distal to bifurcation stenosis in side branch (e.g. LCX)
18. wait for 10 sec for any reactive hyperemia (e.g. due to contrast injection)
19. measure iFR twice (to uncover any upward drift of the value due to remaining reactive hyperemia)
20. measure Pd/Pa in 'FFR mode' for 20 seconds without inducing hyperemia
21. keep wire in position, record angiogram with sufficient contrast filling
22. go in orthogonal view, keep wire in original position, acquire angiogram
23. wait for 10 sec for any reactive hyperemia (e.g. due to contrast injection)
24. measure iFR pullback. Retract the wire into guiding catheter
25. screenshot or short recording to confirm absence of drift, do recording in 'FFR mode' (if drift is more than +/- 0.02, redo normalization and measurement)
